6.9.7 Discontinuation of Therapy

Patients have the right to voluntarily withdraw from the study at any time for any reason. In addition, the investigator has the right to withdraw a patient from the study at any time. Reasons for withdrawal from the study may include but are not limited to the following:

- Patient withdrawal of consent at any time
- Any medical condition or adverse event that the investigator or Sponsor determines may jeopardize the patient's safety if he or she continues in the study
- Investigator or Sponsor determines it is in the best interest of the patient
- Patient non-compliance
- Any significant uncertainty on the part of the Investigator that continued participation is prudent.

Every effort should be made to obtain information on patients who withdraw from the study. The primary reason for withdrawal from the study should be documented on the appropriate eCRF. However, patients will not be followed for any reason after consent has been withdrawn.

Patients who withdraw from the study *after a dose of study therapy has been administered* will not be replaced.

6.9.8 Study Treatment Discontinuation

Patients must discontinue study treatment if they experience any of the following:

- Symptomatic deterioration (i.e., uncontrollable pain secondary to disease) attributed to disease progression as determined by the investigator after integrated assessment of radiographic data, biopsy results, and clinical status.
- Intolerable toxicity related to atezolizumab and/or tiragolumab, including development of an immune-related adverse event (irAE) determined by the investigator to be unacceptable given the individual patient's potential response to therapy and severity of the event
- Any medical condition that may jeopardize the patient's safety if he or she continues on study treatment

- Use of another non-protocol anti-cancer therapy (see Section 5.9)
- Pregnancy
- The primary reason for study treatment discontinuation must be documented in the eCRF.

6.10 Study Calendar

	Screening ^a	All Cycles	Treatment Discontinuation ^b	Post-cystectomy	Follow-Up	Off Study
Assessment Window (Days)	Day -28 to Day -1	Day 1 (± 3 Days for Cycles ≥ 2)	≤ 30 Days after Last Dose, prior to cystectomy	Every 4 weeks (+/- 1 week) x 12 weeks total ^z	Every 12 weeks (+/- 2 weeks)	
Informed Consent	X					
Review of eligibility criteria	X					
Medical, surgical, and cancer histories, including demographic information	X					
Concomitant medication ^c	X	X	X	X	X	X
Adverse events ^d	X	X	X	X	X	X
Tumor tissue acquisition or 15 unstained slides ^e	X			X ^k	X ^k	
Treatment administration						
Atezolizumab infusion ^f (Cohort A)		X				
Atezolizumab and Tiragolumab infusion ^{f,g} (Cohort B)		X				
Clinical procedures						
Complete physical examination ^h	X	X	X	X	X	X
Performance status ^h	X	X	X	X	X	X
Vital signs ⁱ	X	X	X	X	X	X
Oxygen saturation (pulse oximetry)	X	X	X	X	X	X
Tumor assessments ^j	X			X	X	X
Survival and anti-cancer therapy follow-up ^l					X	X
Laboratory procedures^h						
Hematology ^m	X	X	X	X	X	X
Serum chemistry ⁿ	X	X	X	X	X	X
Urinalysis ^o	X	X	X	X	X	X
Urine sample	X	X	X	X	X	X

	Screening ^a	All Cycles	Treatment Discontinuation ^b	Post-cystectomy	Follow-Up	Off Study
Assessment Window (Days)	Day -28 to Day -1	Day 1 (± 3 Days for Cycles ≥ 2)	≤ 30 Days after Last Dose, prior to cystectomy	Every 4 weeks (+/- 1 week) x 12 weeks total^z	Every 12 weeks (+/- 2 weeks)	
Pregnancy test (HCG) ^p	X					
TSH, free T3, free T4	X		X			
HIV, HBV, and HCV Serology ^q	X					
CRP	X	X	X	X	X	X
Serum banking for baseline auto-antibody testing ^r	X					
EBV serology ^s	X					
CK ^t	X					
TBNK blood sample ^u	X	X	X	X	X	X
Plasma, serum, and blood sample for PD biomarkers ^u		X	X	X	X	X
Imaging procedures						
ECG ^v	X					
Chest imaging ^w	X			X ^x	X	X
Bone scan ^x	X					
Abdominal imaging (CT or MRI)	X		X	X ^x	X	X

anti-HBc = hepatitis B core antigen; ATA = anti-therapeutic antibody; EBV = Epstein-Barr virus; HBV = hepatitis B virus, HCV = hepatitis C virus; MRI = magnetic resonance imaging; TBNK = T, B, and NK cells; TSH = thyroid-stimulating hormone; CK = creatine kinase.

Note: Assessments scheduled on the days of study treatment infusions should be performed before the infusion unless otherwise noted.

- Examinations performed as standard of care prior to obtaining informed consent and within 28 days of Cycle 1, Day 1 may be used rather than repeating tests, and within 45 days for radiographic imaging. If patients are declining cisplatin-based chemotherapy the reason must be documented.
- All patients will return within 30 days for a follow up visit, including those who discontinue study therapy early.
- See Section 5.8.
- After informed consent has been obtained but prior to initiation of study drug, only serious adverse events caused by a protocol-mandated intervention should be reported. After initiation of study drug, all adverse events will be reported until 30 days after the last dose of study treatment. After this period, investigators should report any deaths, serious adverse events, or other adverse events of concern that are believed to be related to prior treatment with study drug. The investigator should follow each adverse event until the event has resolved to baseline grade or better, the event is assessed as stable by the investigator, the patient is lost to follow up, or the patient withdraws consent. Every effort should be made to follow all serious adverse events considered to be related to study drug or trial-related procedures until a final outcome can be reported.

- e. Only tumor tissue from initial TURBT and cystectomy are required per protocol. Tumor tissue from TURBT should be of good quality based on total and viable tumor content (sites will be informed if the quality of the submitted specimen is inadequate to determine tumor PD-L1 status). Fine-needle aspiration, brushing, and cytologic cell pellets are not acceptable. For core needle biopsy specimens, at least three cores should be submitted for evaluation. Ideally, a tumor specimen obtained after completion of the most recent therapy should be submitted. Any archival tumor specimen, if available, should also be submitted. **Repeat TURBT or other tumor biopsies are not required after the start of therapy, prior to cystectomy, however if done at any point per local standard of care then all tissue available should be acquired.**
- f. For both atezolizumab and tiragolumab, the initial dose of study drug will be delivered over 60 (\pm 15) minutes. If the first infusion is tolerated without infusion-associated adverse events, the second infusion may be delivered over 30 (\pm 10) minutes. If the 30-minute infusion is well tolerated, all subsequent infusions may be delivered over 30 (\pm 10) minutes.
- g. Tiragolumab dose will be administered following the dose of atezolizumab. If one agent (either atezolizumab or tiragolumab) is held then both study drugs should be held.
- h. ECOG performance status, physical examination, and local laboratory assessments (CBC, serum chemistries, urinalysis) may be obtained \leq 96 hours before the scheduled visit. Laboratory procedures measured within 14 days of beginning treatment do not need to be repeated on Cycle 1 Day 1.
- i. Vital signs include heart rate, respiratory rate, blood pressures, temperature, weight, and oxygen saturation. Height should be recorded once during screening or prior to cycle 1 day 1. For first infusion of study treatment, the patient's vital signs should be determined within 60 minutes before, during (every 15 [\pm 5] minutes), and 30 (\pm 10) minutes after the infusion. For subsequent infusions, vital signs will be collected within 60 minutes before infusion and at the end of the infusion. Patients will be informed about the possibility of delayed post-infusion symptoms and instructed to contact their study physician if they develop such symptoms.
- j. All measurable and evaluable lesions should be assessed and documented at the screening visit. The same radiographic procedure should be used throughout the study for each patient. Available results must be reviewed by the investigator before dosing at the next cycle. Pathologic review of tumor response should occur at the first follow up visit after cystectomy. Patients will undergo assessments for tumor recurrence every 12 weeks (+/- 2 weeks) for the first 2 years following cystectomy. Patients who discontinue from the initial treatment stage for reasons other than disease progression (e.g. toxicity) will continue scheduled tumor assessments until disease recurrence, withdrawal of consent, or death. Patients who start a new anti-cancer therapy in the absence of disease recurrence (e.g. adjuvant therapy) should be followed according to the protocol schedule unless they withdraw consent. Investigators may perform additional scans or more frequent assessments if clinically indicated.
- k. Tumor biopsy at recurrence, preferably at the time of radiographic progression. Patients may opt out of this biopsy. Acceptable samples include core needle biopsies for deep tumor tissue or lymph nodes or excisional, incisional, punch, or forceps biopsies for cutaneous, subcutaneous, or mucosal lesions. For core needle biopsy specimens, at least three cores should be submitted for evaluation.
- l. Survival follow-up information will be collected via telephone calls, patient medical records, and/or clinic visits approximately every 3 months until death, loss to follow-up, withdrawal of consent, or study termination by Sponsor. All patients will be followed for survival and new anti-cancer therapy information unless the patient requests to be withdrawn from follow-up; this request must be documented in the source documents and signed by the investigator. If the patient withdraws from study treatment but not from follow-up, the study staff may use a public information source (e.g., county records) to obtain information about survival status only.
- m. Hematology consists of CBC, including RBC count, hemoglobin, hematocrit, WBC count with automated differential (neutrophils, lymphocytes, eosinophils, monocytes, basophils, and other cells), and platelet count. A manual differential can be done if clinically indicated.
- n. Serum chemistry includes sodium, potassium, chloride, bicarbonate, BUN, creatinine, glucose, calcium, magnesium, phosphorus, total bilirubin, ALT, AST, alkaline phosphatase, total protein, albumin and LDH
- o. Specific gravity, pH, glucose, protein, ketones, and hemoglobin.
- p. Serum pregnancy test (for women of childbearing potential, including women who have had a tubal ligation) must be performed and documented as negative within 14 days prior to Day 1.
- q. HIV testing to be performed in accordance with national and/or institutional guidelines. Hepatitis B surface antigen, anti-HBc antibody and anti-HBs antibody should be collected during screening. In patients who have positive serology for the anti-HBc antibody, HBV DNA should be collected prior to Cycle 1, Day 1.
- r. Serum will be banked and frozen during screening, however these assays will only be run to establish baseline values *if, at a later point in the study, there is clinical suspicion of acute immune-related toxicity related to study drug.*
- s. Perform Epstein-Barr virus (EBV) viral capsid antigen IgM test at screening (See Section 3.3.2 Exclusion Criteria)
- t. Perform creatine kinase (CK) testing at screening, and as clinically indicated as determined by the Investigator
- u. See Appendix 4 for details
- v. ECG recordings will be obtained during screening and as clinically indicated at other timepoints. Patients should be resting and in a supine position prior to ECG collection.

- w. Chest CT is required for screening. Chest X-ray or Chest CT are acceptable in the follow-up phase for surveillance for tumor recurrence, per institutional guidelines. If clinical suspicion of recurrent disease in the chest a CT scan should be performed.
- x. Bone scan (Technetium or Sodium-fluoride PET/CT required at screening only for subjects with an elevated alkaline phosphatase or clinical suspicion of bony metastatic disease. Further imaging for subjects on study only as clinical indicated.
- y. Chest and abdominal imaging at the 12 week post cystectomy visit, does not need to be done earlier unless clinically warranted

7 Reporting and Documentation of Results

7.1 Evaluation of Efficacy

7.1.1 Pathologic Response

Treatment efficacy will be determined by the pathologic determination of tumor response at the time of cystectomy. This will include determination of tumor response in the bladder as well as in any resected lymph nodes.

Pathologic determination should be in accord with collaborative guidelines³³ and should specifically proceed as follows:

For all cystectomy specimens the pathologist will cut the tissue at roughly 0.5cm intervals to look for a tumor mass. If no tumor mass is seen on gross examination then representative sections should be put in. If cystoscopic abnormalities are noted by the treating Urologist, then the treating Urologist will indicate location of cystoscopic abnormalities (up to 4 different ones) on the pathology requisition, and that pathologists will "block in" each of these areas (up to 4 different areas) during pathologic evaluation of the bladder to cover at least 1 cm square area of each indicated location. This is in addition to any grossly-recognized residual tumor foci that are seen when opening the bladder for pathologic evaluation.

It is similarly recommended that prior surgical sites or mucosal ulcerations be sampled in their entirety for residual tumor and adequate mapping performed. Furthermore, areas that appear red and regions of mucosal induration should be sampled to rule out CIS. There is no need for complete embedding of the entire bladder wall. Communication between the urologic surgeon and pathologist is key in cases where prior surgical sites, mucosal ulcerations, or alterations are not evident to ensure that appropriate tissue sampling occurs.

The following definitions apply to determination of pathologic responses:

Evaluable for pathologic complete response

Only those patients who have received at least one cycle of therapy, and have had their disease evaluated pathologically at the time of resection will be considered evaluable for pathologic response. These patients will have their response classified according to the pathologic complete response definitions below:

- **Pathologic complete response (pCR):** Defined as the presence of pT0 disease. Similarly there must be no evidence of tumor in all resected lymph nodes (N0).
- **Near pathologic complete response (near pCR):** Defined as the presence of Ta or Tis disease (or both) in the resection specimen, without evidence of any higher stage disease elsewhere or evidence of tumor in all resected lymph nodes (N0).

All patients will be followed for 2 years post-cystectomy to evaluate for tumor recurrence.

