5.9 Excluded Therapy

Any concomitant therapy intended for the treatment of cancer, whether health authority-approved or experimental, is prohibited. This includes but is not limited to the following:

- Chemotherapy, hormonal therapy, immunotherapy, radiotherapy, investigational agents, or herbal therapy (except for maintenance therapies outlined in section 5.8).
- Traditional herbal medicines should not be administered because the ingredients of many herbal medicines are not fully studied and their use may result in unanticipated drug-drug interactions that may cause or confound assessment of toxicity
- Patients who are receiving a receptor activator of nuclear factor kappa B ligand (RANK- ligand) inhibitor (denosumab) prior to enrollment must be willing and eligible to receive a bisphosphonate instead while on study;

denosumab could potentially alter the activity and the safety of the study drugs.

- Initiation or increased dose of granulocyte colony-stimulating factors (e.g. granulocyte colony-stimulating factor, granulocyte/macrophage colony-stimulating factor, and/or pegfilgrastim) is strongly discouraged.
- Patients are not allowed to receive immunostimulatory agents, including but not limited to interferon (IFN)- α , IFN- γ , IL-2, or ipilimumab during the entire study. These agents, in combination with the study drugs, could potentially increase the risk for autoimmune conditions.
- Patients should also not receive immunosuppressive medications, including but not limited to cyclophosphamide, azathioprine, methotrexate, and thalidomide. These agents could potentially alter the activity and the safety of the study drugs. Systemic corticosteroids and anti-TNF- α agents may attenuate potential beneficial immunologic effects of treatment with the study drugs but may be administered at the discretion of the treating physician after consultation with the Study Chair. If feasible, alternatives to these agents should be considered.
- In addition, all patients (including those who discontinue the study early) should not receive any other immunostimulatory agents for 10 weeks after the last dose of the study drugs.
- Patients who receive local therapy directed at the bladder (i.e., repeat TURBT, radiation therapy) after study treatment initiation but prior to cystectomy will be considered ineligible for response evaluation, but will remain eligible for safety and correlative evaluation. Such cases must be discussed with and approved by the Study Chair.

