8.1 Determination of Sample Size and Power Calculation

Cohort A

Multi-dose phase: With 6 patients in each cohort, there will be 80% of power to detect the effect size of 1.5 at significance level of 0.1. For the lowest dose level, a 2-fold increase from pre-treatment to post- treatment is expected, if at the higher dose level, there is more than 3-fold increase, assuming the standard deviation equals 1, then there will be 80% power to detect significant treatment effect on the intratumoral immune response.

Expansion phase: Data from a study of intravesical valrubicin chemotherapy in BCG refractory patients³⁴ demonstrated that a 21% CR rate is achievable at 6 months. Assuming a 5% (null) CR rate for untreated patients at 6 months, 15 patients would be required to observe an improvement to a 36% CR rate at 6 months in response to-PD-L1 therapy (effect size = 0.642), at a significance level of 0.1 with 80% power.

Cohort B

A pT0 rate at cystectomy was observed for ~30% of patients treated with immune checkpoint inhibitors monotherapy based on published Phase II clinical trials. In order to observe an improvement from a 30% CR rate (null hypothesis) to 60% CR rate (alternative hypothesis) with the combination of atezolizumab and tiragolumab a total of 21 patients are required in Cohort B assuming a significance level of 0.05 and 80% power.

Using these assumptions, following a lead in safety phase of 6 patients at a combination regimen that is deemed to be safe based on the criteria outlined above, a further 15 patients will be enrolled at the same regimen. This will make a total of 21 patients to be treated in Cohort B with the intended regimen.

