8.3 Analysis Plans

8.3.1 Analysis Population

All patients who receive any part of a dose of any study drug will be analyzed for safety and efficacy. Subjects who discontinue from study participation prior to receiving any dose of study therapy may be replaced after discussion with the Study Chair. Subjects who have received any dose of study therapy will not be replaced.

Demographic and baseline characteristics will be summarized. In general, frequency distribution and percentage will be used to summarize categorical measurements, while mean with standard deviation and median with range will be used to describe symmetric and skewed continuous measurements, respectively. Univariate analysis among variables will be assessed using the two-sample t-test, Wilcoxon-rank-sum test, Chi-square test, as appropriate.

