8.3.2 Analysis of Primary Endpoints

The immunologic effect of activity study therapy within bladder tissue will be measured by a change in the CD3⁺ T cell count/ μm^2 between the pretreatment biopsy and the cystectomy tissue following study therapy administrations. Immunohistochemistry will be performed in the [name] lab at UCSF per established SOPs. Based on prior experience tissue will be designated into 3 distinct compartments: benign epithelium, tumor centers, and tumor interfaces. Tumor interfaces will be defined as fields where malignant and benign epithelium are present. Automatic cell counts for single- and double-stained cells will be determined for each field with color-specific algorithms.

The cell count for each compartment will be reported as the mean for each of the five quantitated fields. Cells of interest will include CD3⁺ T cells, CD3⁺ Ki67⁺ proliferative T cells,

CD4+ FoxP3- helper T cells, CD4+ FoxP3+ regulatory T cells, CD8+ cytotoxic T cells, as well as PD-1 expression on the different lymphocytes. In collaboration with Genentech, PD-L1 expression on both tumor and immune cells within the microenvironment will be assessed.

For each cohort, the change of T cell counts from pre-treatment to post-treatment will be calculated for each compartment as log2 of the ratio of post-treatment vs. pre-treatment counts. If different regimens are used (for example atezolizumab x 3 doses and tiragolumab x 2 doses) two-sample Wilcoxon rank sum test will be used to compare the difference of the change from pretreatment to post-treatment between cohorts to assess if the intratumoral immune response associated with increasing numbers of treatments. No multiple comparison adjustments will be performed.

8.3.2.1 pT0 rate

Point estimates and 95% confidence intervals of pathologic T0 rate at the time of cystectomy as defined in Section 7.1.1 will be obtained for subjects treated with atezolizumab and tiragolumab. Pathologic T0 rate at the time of cystectomy will be compared with the null hypothesis rate (see Section 8.1) separately by using one-sample proportion test.

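### The Cohort B primary pT0N0 rate has conflicting population rules, and no section says how a dosed patient without cystectomy pathology, or with prior local bladder therapy, is scored

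*Combined protocol and SAP*

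**What the plan says.** - **Section 8.3.1** sets the analysis population: "All patients who receive any part of a dose of any study drug will be analyzed for safety and efficacy". It adds: "Subjects who have received any dose of study therapy will not be replaced".
- **Section 8.1** sizes Cohort B on the same footing: "This will make a total of 21 patients to be treated in Cohort B with the intended regimen". Its null rate is worded similarly: "A pT0 rate at cystectomy was observed for ~30% of patients treated with immune checkpoint inhibitors monotherapy".
- **Section 7.1.1** is narrower. Only patients who received at least one cycle and "have had their disease evaluated pathologically at the time of resection will be considered evaluable for pathologic response" have their response classified.
- **Section 5.9** says that patients given local therapy to the bladder (repeat TURBT or radiation) after starting study treatment and before cystectomy "will be considered ineligible for response evaluation, but will remain eligible for safety and correlative evaluation". Such cases need the Study Chair's approval.
- **Section 8.3.2.1** plans a point estimate, a 95% confidence interval and a one-sample proportion test for the pT0 rate, which "as defined in Section 7.1.1 will be obtained for subjects treated with atezolizumab and tiragolumab". The endpoint in section 2.1 also refers to 7.1.1.
- The ITT population is named for RFS and OS (sections 2.2 and 8.3.3.1), but not for pT0.

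**The concern.** Two analysts who each follow the text can report different primary rates from the same data. One divides by everyone dosed. The other divides by the 7.1.1 evaluable set less the 5.9 patients. The second route drops treated patients who were not replaced, because of something that happened after baseline. If those without pathology are in truth non-responders, the rate is inflated. For 5.9 patients the direction is unknown, because they may still be resected and found pT0N0.

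Following 8.3.1 alone does not settle it, because 7.1.1 gives no response category to a dosed patient who has no cystectomy specimen. The trial is open-label and single-arm, so a choice left open until the pathology is known could be influenced by the results.

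**Working it through.** **Inputs.** Null 30%, alternative 60%, significance level 0.05, power 80%, N = 21 (section 8.1). The test is a one-sample proportion test, with neither sidedness nor exact versus normal form stated (section 8.3.2.1). The number of dosed patients without pathology, m, is not in the documents. I take m = 1 or 2 for illustration and, under the all-treated rule, count these patients as not pT0N0.

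**The plan's own figure.** The two-sided arcsine formula gives h = 2·arcsin√0.60 − 2·arcsin√0.30 = 0.613, and n = (1.960 + 0.842)² / h² = 20.9, so 21. This reproduces section 8.1. It assumes that 21 patients are analysed.

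**Estimate and interval (exact 95%).** With 12 responses:
- 12/21 = 57.1% (34.0 to 78.2)
- 12/19 = 63.2% (38.4 to 83.7)

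Once there is at least one response, any excluded patient moves these figures, wherever the cut-off lies.

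**Test conclusion.** Score statistic z = (x/n − 0.30) / √(0.30 × 0.70 / n).

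| Responses | z | Two-sided score p | Exact one-sided p |
|---|---|---|---|
| 10/21 | 1.76 | 0.078 | 0.068 |
| 10/20 | 1.95 | 0.051 | 0.048 |
| 10/19 | 2.15 | 0.031 | 0.033 |
| 11/21 | 2.24 | 0.025 | 0.026 |

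With 10 responses, two exclusions reverse the score-test result at 0.05. One exclusion reverses the exact one-sided result, which the plan does not rule out. At 11 or more responses both denominators reject.

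**Error and power with m = 2.** Score cut-offs are 11/21 and 10/19. The figures are upper-tail probabilities, to be compared with 2.5% per side.
- *30% is an all-treated rate.* The rate among the 19 resected patients is then 0.30 × 21/19 = 0.332. Evaluable denominator: P(X ≥ 10 | 19, 0.332) = 6.3%. All-treated denominator: P(X ≥ 11 | 19, 0.332) = 2.3%.
- *30% is a resected-patient rate.* The same two probabilities at 0.30 are 3.3% and 1.1%, so the excess is much smaller.
- *60% is a resected-patient rate.* Power is P(X ≥ 10 | 19, 0.60) = 81% with the evaluable denominator and P(X ≥ 11 | 19, 0.60) = 67% with all treated. With nobody missing, P(X ≥ 11 | 21, 0.60) = 83%.

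**A 5.9 patient.** Suppose one such patient is resected and pT0N0, and 10 of the other 20 are pT0N0. Scored as a response this is 11/21 (score p = 0.025). Excluded, it is 10/20 (p = 0.051). Scored as not pT0N0, it is 10/21 (p = 0.078). The scoring rule alone decides the result.

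**The case against.** The best defence is that section 8.3.1, under the heading for the analysis population, already answers the question. On that reading the pointer to 7.1.1 in 8.3.2.1 only defines what pT0 means, and the phrase about treated subjects names the population. This is a fair reading and largely stands: the statistical chapter leans all-treated. A reader might infer that the plan has no denominator, or that it intends an evaluable-only analysis. The documents do not support either. What survives is that 7.1.1 and 5.9 still take patients out of response evaluation, and nothing says how those patients are scored if they stay in.

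The second defence is that few patients will be affected. Cystectomy is planned for everyone (section 5.1.1), toxicity that would delay surgery past 12 weeks sends the patient to cystectomy (section 5.6), and 5.9 cases need approval. The only cited figure, from the neoadjuvant pembrolizumab trial in section 1.5, is that all 50 patients were resected. So a reader should not infer that substantial loss is expected. Losses are still possible, because section 6.9.7 says "patients will not be followed for any reason after consent has been withdrawn" and dosed patients are not replaced. The follow-up rule in section 6.9.4 for patients who stop before cystectomy concerns stopping drug, so it is weak evidence that surgery will be missed.

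The opposite inference, that the issue matters only near the decision boundary, is also wrong. It holds for rejecting or not rejecting, but not for the planned estimate and interval.

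**Conclusion.** The conflict stands and should be fixed before the primary analysis. It is a gap in the rules for a primary endpoint and does not invalidate the design.

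The conflict in the text is certain, but its numerical effect is conditional. The estimate and interval change with any excluded patient once there is a response. The test conclusion changes only near the cut-off: at 10 responses, with two exclusions under the score test or one under the exact one-sided test. The rise in upper-tail error to 6.3% assumes two unresected non-responders, score cut-offs, and 30% as an all-treated rate. The fall in power from 81% to 67% assumes two unresected patients and 60% as a resected-patient rate. Section 8.1 words the 30% as a rate among treated patients, but does not say how unresected patients were counted in it or in the 60%. If nobody lacks pathology and no 5.9 case occurs, the two denominators coincide, provided every patient also meets the one-cycle condition in 7.1.1.

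**What to change.** State the following in 8.3.2.1, and align 7.1.1 and 5.9 with it:

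> The primary pT0N0 rate is the number of patients scored as pT0N0 divided by all patients who received any study drug at the established regimen. Patients without cystectomy pathology, and patients who received bladder-directed local therapy before cystectomy (section 5.9), stay in the denominator and are counted as not pT0N0.

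Report two labelled sensitivity analyses: one with 5.9 patients scored by their actual cystectomy pathology, and one in the 7.1.1 evaluable set. State in 8.1 whether 30% and 60% are all-treated rates. If 60% is a resected-patient rate, restate the power.

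The cost is wording in four sections, with no new data. The primary rate will be equal to or lower than the evaluable-set rate. Power will also be lower if the 60% refers to resected patients and some patients are not resected.
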